11.6.	Randomization and Treatment Assignment	20
11.7.	Treatment Compliance	21
11.8.	Recording Data	21
11.9.	Deviation Handling.....	21
11.10.	Subject Withdrawal or Discontinuation	22
12.	Risks and Benefits	22
12.1.	Potential Risks	22
12.2.	Potential Benefits	24
12.3.	Risk-Benefit Rationale.....	24
13.	Adverse Event Assessments.....	24
13.1.	Definitions/Classifications	24
13.2.	Reporting of Adverse Events	25
13.3.	Post Market Surveillance	27
13.3.1.	Definition of Product Complaint:	27
13.3.2.	Reporting of product complaints	27
14.	Advisory Committees	27
15.	Statistical Design and Methods	28
16.	Ethics	28
16.1.	Statement(s) of Compliance.....	28
17.	Study Administration.....	29
17.1.	Monitoring	29
17.2.	Data Management.....	29
17.3.	Confidentiality.....	29
17.4.	CIP Amendments	30
17.5.	Investigator record retention.....	30
17.6.	Sponsor record retention.....	31
17.7.	Publication and Use of Information.....	31
17.8.	Suspension or Early Termination	32
18.	References.....	32

This document is electronically controlled. Printed copies are considered uncontrolled.

Confidential

3. Glossary

Term	Definition
MASS	Micra Accelerometer Sensor sub-Study
ECG	Electrocardiogram
MASS2	Micra Accelerometer Sensor Study 2
MATS	Micra Accelerometer and Temperature Sensor
E-CRF	Electronic Case Report Form
EDC	Electronic Data Capture
ICF	Informed Consent Form
EC	Ethics Committee
CIP	Clinical Investigation Plan
CTA	Clinical Trial Agreement
CV	Curriculum Vitae
ISF	Investigator Site File
LVOT	Left Ventricular Outflow Track
VTI	Velocity Time Integral
IC	Informed Consent
AE	Adverse Event
ADE	Adverse Device Effect
SAE	Serious Adverse Event
SADE	Serious Adverse Device Effect
USADE	Unanticipated Serious Adverse Device Effect

This document is electronically controlled. Printed copies are considered uncontrolled.

Confidential

Term	Definition
CEC	Clinical Event Committee
GCP	Good Clinical Practice

This document is electronically controlled. Printed copies are considered uncontrolled.

Confidential

4. Synopsis

Title	Micra Accelerometer Sensor Study 2 (MASS2)		
Clinical Study Type	Prospective non-randomized, multi-center clinical research study.		
Product Name	MATS Research System		
Sponsor	Medtronic, Inc. [name] [contact]		
Local Sponsor	Bakken Research Center B.V. [name] [contact]		
Manufacturer	Medtronic, Inc. [name] [contact] [contact]		
Investigation Purpose	The purpose of the MASS2 is to characterize accelerometer signals of Micra implantable device during different postures and activities and to understand the source of the sensed motion, in order to test feasibility for future enhancements in device functionalities.		
Product Status	Model Number	Component (Manufacturer)	Investigational or Commercially available
	MC1VR01	Micra™ Implantable Device (Medtronic)	Commercially available in Europe
	2090	Medtronic Carelink Programmer (Medtronic)	Commercially available in Europe
	SW022	Micra™ Software Version 1.1 (Medtronic)	Commercially available in Europe
	No model number	MATS Software Version 1.0 (Medtronic)	Investigational

This document is electronically controlled. Printed copies are considered uncontrolled.

Confidential

	Model Number	Component (Manufacturer)		Investigational or Commercially available	
	ER220	Extended Range Holter Monitor System (Medtronic)	DR220 Holter (Medtronic)	Commercially available in Europe	
			ERX10 Extended range Tel-B antenna cable (Medtronic)	Investigational	
Primary Objective	The primary objective of MASS2 is to collect and characterize the waveform and components of the accelerometer signal from the Micra implantable device during different postures and activities, and to use echocardiography recordings to understand the elements contributing to the accelerometer signal				
Study Design	
The MASS2 is designed to extend and advance data collection of its predecessor, the MASS study.
 
The MASS2 study will be conducted in Europe and may include countries such as Austria, France and Spain. The study is expected to be conducted at approximately four centers.
 
The target population will consist of subjects aged ≥ 18 and implanted with a Micra device and not in Atrial Fibrillation. The expected duration of subject participation to the study (from enrollment until the exit of the subject) is approximately 2 hours.
 
The expected total study duration (from the enrollment of first subject to the exit of last subject) is approximately 6 months, representing the months of enrollments.
				
Sample Size	Between 40 and 50 subjects are planned to be enrolled in the MASS2 in order to collect a representative sample of approximately 40 readable datasets. Centers that enroll faster than others will be allowed to do so in order to maintain an adequate enrollment rate, and therefore there is not a minimum or maximum requirement for the number of subjects enrolled at each center.				
Inclusion/Exclusion Criteria	
Inclusion Criteria
 
 • Subject is ≥ 18 years old • Subject is implanted with a Micra device • Subject or witness (if applicable as per local regulation) is able and willing to provide Informed Consent 
Exclusion Criteria
 
 • Subject is in atrial fibrillation • Subject is not able to perform study requirements 				
Study Procedures and Assessments	After subject enrollment, the investigational MATS software will be downloaded into the implanted Micra device and the subject will be equipped with the Holter for the time of a posture and exercise test. As in MASS, the MATS software will allow telemetry transmission of sensor data from the implanted Micra device to the				

This document is electronically controlled. Printed copies are considered uncontrolled.

Confidential

	
Holter.
 
After the posture and exercise test, subject will undergo the echo recording with the echo equipment available at the hospital.
 
After the echo recording, the Holter will be removed from the subject and the MATS software will be manually removed from the Micra device. After the software removal, the subject will be exited from the study.

Safety Assessments	
Based on the risk assessment of the MATS Research System and results from the previous MASS study, there are no anticipated or foreseeable adverse events expected to be related to MASS2 products or procedures.
 
MASS2 will allow collection of all adverse events and device deficiencies. Medtronic will classify each adverse event according to ISO 14155:2011.

Statistics	
Since the study will be exploratory in nature, subjects will be enrolled to collect a representative sample of approximately 40 readable datasets.
 
Study objective is descriptive and therefore no endpoints will be developed.

This document is electronically controlled. Printed copies are considered uncontrolled.

Confidential

5. Introduction

5.1. Background

Rate adaptive pacing may improve exercise capacity in subjects with chronotropic incompetence [1-5]. A number of sensors have been used to adjust pacing rate for rate adaptive pacing [6]. Medtronic rate adaptive pacing algorithms use a single axis accelerometer to adjust pacing rate during activity. Micra device is a single chamber ventricular pacemaker implanted in the right ventricle which uses a three-axis accelerometer. The recordings from all three accelerometer vectors may provide information on subject posture and allow for determination of the optimal accelerometer vector to be used for rate adaptive pacing. The accelerometer of Micra device is also capable of sensing heart motion and thus may detect atrial and ventricular contraction. Characterization of the intracardiac accelerometer signal may allow for the development of methods to synchronize ventricular pacing with atrial contractions, and consequently, the ability to provide atrioventricular synchronized pacing. This would potentially broaden the pacemaker indications for which the Micra implantable device may be used.

A previous clinical research study called the Micra Accelerometer Sensor sub-Study (MASS) collected accelerometer data and electrical heart activity of subjects implanted with a Micra device, during various postures and 24 hours of daily living. MASS used electrocardiogram (ECG) data to characterize accelerometer signal as motion associated with the atrial contraction. However, the source of the motion sensed by the accelerometer remains unclear. Understanding the source of the sensed motion may allow for the development of methods to synchronize ventricular pacing with atrial contractions. The recording of cardiac echo data, in addition to ECG data, may help to understand the elements contributing to the sensed activity and consequently may provide the ability to deliver atrioventricular synchronized pacing. This would potentially broaden the pacemaker indications for which the Micra implantable device may be used.

5.2. Purpose

The purpose of the Micra Accelerometer Sensor Study 2 (MASS2) is to characterize accelerometer signals of Micra implantable device during different postures and activities and to understand the source of the sensed motion, in order to test feasibility for future enhancements in device functionalities.

6. Objectives and Endpoints

6.1. Objective

The primary objective of MASS2 is to collect and characterize the waveform and components of the accelerometer signal from the Micra implantable device during different postures and activities, and to use echocardiography recordings to understand the elements contributing to the accelerometer signal.

This objective is descriptive and therefore no endpoints will be developed.

There are no secondary objectives (therefore no secondary endpoints) for MASS2.

7. Study Design

The MASS2 is a prospective non-randomized, multi-center clinical research study, designed to extend and advance data collection of its predecessor, the MASS study.

This document is electronically controlled. Printed copies are considered uncontrolled.

Confidential

The study will be conducted in Europe and may include countries such as Austria, France and Spain. The study is expected to be conducted at approximately four centers. Between 40 and 50 subjects are expected to be enrolled in order to collect a representative sample of approximately 40 readable datasets. Since the study will be exploratory in nature, no statistical hypotheses were formulated to calculate the sample size and the number of expected subjects was based on the experience from the previous MASS study.

Centers that enroll faster than others will be allowed to do so in order to maintain an adequate enrollment rate, and therefore there is not a minimum or maximum requirement for the number of subjects enrolled at each center.

The Micra Accelerometer and Temperature Sensor (MATS) Research System was developed in support of the MASS study to allow collection of data from the Micra sensors. MASS2 will use the unchanged MATS Research System for the same purposes of MASS.

MASS2 procedures will be similar to MASS. After subject enrollment, the investigational MATS software will be downloaded into the implanted Micra device and the subject will be equipped with the Holter for the time of the posture and exercise tests. As in MASS, the MATS software will allow telemetry transmission of sensor data from the implanted Micra device to the Holter. The additional procedure introduced in MASS2 compared to MASS is the echocardiography recording. The echo recording will be done after the posture and exercise test using the echo equipment available at the hospital. The collected echo recordings will be used to understand the source of the signals from the intracardiac accelerometer. After the echo recording, the Holter will be removed from the subject and the MATS software will be manually removed from the Micra device. After the software removal, the subject will be exited from the study. The Holter overnight recording, which was optional in MASS, will not be part of MASS2.

Every effort will be undertaken to minimize missing data (e.g. periodic assessment of the accelerometer, ECG and echo data).

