7.2. Rationale

The previous MASS study was developed to collect data from the sensors of the Micra device, using the MATS Research System. All pre-clinical testing on the MATS Research System were executed in support of the MASS study and the results showed that all tests have successfully passed. MASS study enrolled 40 subjects. Neither adverse events nor device deficiencies related to MASS system/procedures were reported during the MASS study. Usable recordings were obtained from 32 of the subjects. The continuous accelerometer signal was used to develop a preliminary algorithm to detect atrial contractions using the accelerometer in the right ventricle. The 20 recordings in sinus rhythm were processed and the accuracy of the atrial detection algorithm was assessed. A larger sinus rhythm data set is desired for a wider representation of subjects and for further algorithm development. Therefore, MASS2 is being proposed to record additional subjects to extend the data set, using the unchanged MATS Research System. Furthermore, MASS2 will also collect echocardiography recordings to characterize the source of the accelerometer signal from the intracardiac accelerometer.

With the FDA and CE approval of the Micra device and the resulting launch of closure activities of the Micra Transcatheter Pacing Study (IDE Number: G130245), MASS2 is designed as an independent/stand-alone study.

This document is electronically controlled. Printed copies are considered uncontrolled.

Confidential

8. Product Description

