 - Walking at a normal pace for 2-3 minutes

This document is electronically controlled. Printed copies are considered uncontrolled.

Confidential

Subject is allowed to have recovery time during the test as needed. If no recovery is needed, it is possible to move to the next exercise as soon as the subject is ready. In case part of the test cannot be completed, this should not be considered a deviation.

The Holter will allow recording of ECG and accelerometer data during the posture and exercise test, for each of the three rate response activity vectors.

- **Echo examination** - After the posture and exercise test is completed, subject will undergo the echo recording: 4 chamber, left atrial volume, left ventricular outflow track (LVOT) velocity time integral (VTI), pulmonic valve VTI, mitral flow, tricuspid flow. During echo recording, accelerometer data will continue to be recorded on the ER220 Holter. In case the Holter electrodes complicate the echo examination, the electrodes can be moved. After the echo recording, Holter will be removed and Holter telemetry will be set OFF.
- **MATS software removal** - After the echo examination, the Holter will be removed from the subject and the MATS software will be manually removed from the implanted Micra device, using the programmer.
- **Subject exit** – After removal of MATS software, subject will be exited. (Note: in case the MATS software was not manually removed, the subject will be exited after the automatic deactivation of the software).

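### Does the enrolment of 40 to 50, taken from a study without echo, leave too few datasets for the echo part of the objective?

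*Combined protocol and SAP*

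**What the plan says.** - **Size and its basis (Section 7).** The plan reads: "Between 40 and 50 subjects are expected to be enrolled in order to collect a representative sample of approximately 40 readable datasets". No hypothesis was used, and "the number of expected subjects was based on the experience from the previous MASS study".
- **MASS yield (Section 7.2).** MASS enrolled 40 subjects, and "Usable recordings were obtained from 32 of the subjects". Of these, 20 were in sinus rhythm. The causes of the 8 losses are not given.
- **Role of echo.** The second half of the primary objective (Section 6.1) is "to use echocardiography recordings to understand the elements contributing to the accelerometer signal". Section 7 adds: "The additional procedure introduced in MASS2 compared to MASS is the echocardiography recording".
- **Procedures (Section 11).** The accelerometer keeps recording during echo. On interference between the two: "In case the Holter electrodes complicate the echo examination, the electrodes can be moved". On the posture and exercise test: "In case part of the test cannot be completed, this should not be considered a deviation". On the order of procedures: "After the posture and exercise test is completed, subject will undergo the echo recording".
- **Deviations and withdrawal.** Section 11.9 mentions subject inability among situations needing no prior approval, and lists missing ECG, accelerometer or echo data as a deviation. Section 11.10 gives inability to complete the test as one possible reason for withdrawal, and allows withdrawn subjects to be replaced.
- **Oversight and reporting.** Sections 7 and 11.7 provide for periodic review of Holter and echo data. Section 15 plans no imputation, no hypothesis test and no interim analysis, and reports the number of subjects in each analysis.

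**The concern.** The count of about 40 readable datasets is the only size target in the plan, and the plan does not define it. MASS can inform the yield of accelerometer and ECG recordings, but it says nothing about echo. If the gap between 40 and 50 is there to absorb recording loss at the MASS rate, it is fully spent before any echo proves unreadable. Enrolment could then close with about 40 recordings and fewer echo-accelerometer pairs, and the pairs are the new means of finding the source of the signal. The replacement rule is written for withdrawn subjects. It does not mention someone who finished the visit and whose echo later turns out to be unreadable.

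The handling of an unfinished posture and exercise test also looks inconsistent: not a deviation in Section 11, apparently one in Section 11.9, and grounds for withdrawal with replacement in Section 11.10. If such subjects are replaced, less fit subjects could drop out of a sample meant to be representative. If they are kept, they stay in it.

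**Working it through.** **Inputs.** Target about 40 and enrolment 40 to 50 (Section 7); MASS 32 usable of 40 (Section 7.2). Readable is taken to mean the same as usable in MASS, which is an assumption. Echo yield e, among subjects with a usable recording, is not in the documents; the assumed range is 100, 95, 90 and 80%.

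**1. The plan's own figure.** Yield = 32/40 = 0.80, and 40/0.80 = 50, which is the upper end of the range. At 45 enrolled the expected count is 45 × 0.80 = 36, and at 40 it is 40 × 0.80 = 32. The plan does not state 0.80 as its planning rate; this is an inference from the match.

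**2. Uncertainty in the MASS rate.** The exact 95% interval for 32/40 is 0.64 to 0.91. Fifty enrolled then give about 32 to 45 recordings before echo is considered.

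**3. If a dataset must include a readable echo.** Expected pairs = n × 0.80 × e. The probabilities are binomial with n = 50. Counting 36 or more as about 40 is an assumption.

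| Assumed e | Expected, n = 50 | Expected, n = 45 | P(36 or more) | P(40 or more) | n for an expected 40 |
|---|---|---|---|---|---|
| 100% | 40 | 36 | 0.94 | 0.58 | 50 |
| 95% | 38 | 34 | 0.80 | 0.32 | 53 |
| 90% | 36 | 32 | 0.57 | 0.13 | 56 |
| 80% | 32 | 29 | 0.15 | 0.01 | 63 |

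**4. How far this rests on its assumptions.** With 10% echo loss overall, the expected count at 50 enrolled is 50 × (0.80 + 0.90 − 1) = 35 if echo and recording losses never fall on the same subject. It is 40 if every echo loss falls on a subject already lost. A recording yield of 0.80/0.90 = 0.89, which is inside the MASS interval, would give 40 pairs even with 10% independent echo loss.

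**5. What a shortfall costs.** For a descriptive mean the standard error scales as 1/√n. Against 40 pairs:

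- 38 pairs: √(40/38) = 1.03
- 36 pairs: √(40/36) = 1.05
- 32 pairs: √(40/32) = 1.12

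The standard error is 3, 5 or 12% larger, and no precision target is stated that this could breach.

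**6. The passages on an unfinished test, side by side.** Section 11 speaks specifically of part of the test. Section 11.9 gives general examples, and data can be missing for other reasons, such as a computer fault. Section 11.10 lists possible reasons for withdrawal and does not require it. The sentence placing echo after the test can be read as giving the order of procedures, as Section 7 does, without making completion a condition for echo. On that reading the passages can stand together. Section 15 defines no analysis set by deviation status, so that label alone removes nobody from an analysis.

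**The case for a change.** The best argument for a change is that the safeguards act late or on the wrong subjects. Subjects exit on the day of the visit, data are reviewed after they are received, and the replacement examples are failed software download and failed Holter telemetry. An unreadable echo in a completer therefore falls outside the written replacement rule, and reporting the number per analysis discloses a shortfall without preventing it. Enrolment at the low end, 40, would give an expected 32 recordings even with perfect echo. Defining the target would cost a few lines of text.

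Part of this stands. The term is undefined, no echo yield is given, and the plan is silent on completers with unreadable data and on whether replacements may take enrolment above 50. The sections on the unfinished test could be worded more consistently.

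The argument for a shortfall is weaker. Section 15 has subjects enrolled in order to reach the target, so the target drives enrolment, and the range is described as planned or expected. Periodic review during about 6 months of enrolment can show echo losses while recruitment is still possible. Some of the 8 MASS losses may have been technical failures of the kind Section 11.10 allows to be replaced, in which case applying the full 20% overstates the loss. Moving electrodes lets the echo go ahead and is no evidence that echo will fail. Subjects unable to perform the study requirements are already excluded (Section 9.4), which limits any selection through withdrawal.

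**Conclusion.** No change is needed. The stated enrolment is consistent with MASS for accelerometer and ECG recordings. Section 7.2 presents the larger dataset as serving wider representation and algorithm development, and introduces echo as an addition. A shortfall appears only if the target is read as paired datasets, an echo loss not given in the documents is assumed, and 50 is treated as a ceiling.

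Even then, echo yields of 95 and 90% give an expected 38 and 36, which can reasonably count as about 40. An 80% yield gives 32, which is clearly short, but its effect in this study is a standard error about 12% larger for a descriptive summary. These figures assume a true recording yield of 0.80 and echo loss independent of recording loss.

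With no hypothesis, endpoint or precision target, and with the number in each analysis reported, following the plan as written still gives sound descriptive results. Analysts can report the recording count and the paired count separately under Section 15 as it stands. Enrolling 3, 6 or 13 more subjects (for assumed yields of 95, 90 or 80%) would alter no conclusion that the plan sets out to draw.

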7.1. Duration

The expected total study duration (from the enrollment of first subject to the exit of last subject) is approximately 6 months, representing the months of enrollments. The expected duration of subject participation to the study (from enrollment until the exit of the subject) is approximately 2 hours.

7.2. Rationale

The previous MASS study was developed to collect data from the sensors of the Micra device, using the MATS Research System. All pre-clinical testing on the MATS Research System were executed in support of the MASS study and the results showed that all tests have successfully passed. MASS study enrolled 40 subjects. Neither adverse events nor device deficiencies related to MASS system/procedures were reported during the MASS study. Usable recordings were obtained from 32 of the subjects. The continuous accelerometer signal was used to develop a preliminary algorithm to detect atrial contractions using the accelerometer in the right ventricle. The 20 recordings in sinus rhythm were processed and the accuracy of the atrial detection algorithm was assessed. A larger sinus rhythm data set is desired for a wider representation of subjects and for further algorithm development. Therefore, MASS2 is being proposed to record additional subjects to extend the data set, using the unchanged MATS Research System. Furthermore, MASS2 will also collect echocardiography recordings to characterize the source of the accelerometer signal from the intracardiac accelerometer.

With the FDA and CE approval of the Micra device and the resulting launch of closure activities of the Micra Transcatheter Pacing Study (IDE Number: G130245), MASS2 is designed as an independent/stand-alone study.

This document is electronically controlled. Printed copies are considered uncontrolled.

Confidential

8. Product Description

